5.2.1 Eligible cohort entry dates

Market availability of dabigatran in the U.S. for non-valvular atrial fibrillation started on October 19, 2010

- For Medicare: October 19, 2010 – December 31, 2017 (end of available data)
- For Marketscan: October 19, 2010 – December 31, 2018 (end of available data)
- For Optum: October 19, 2010 – December 31, 2019 (end of available data)

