Excluded based on Exclusion 10 & 11 - Pregnancy & Anemia and Thrombocytopenia	-191	25,673	-1,229	82,993	-2,798	163,724
Excluded based on Exclusion 14 - Alcohol abuse or dependence	-28	25,645	-103	82,890	-138	163,586
Excluded based on Exclusion 14 - Drug abuse or dependence	-22	25,623	-47	82,843	-111	163,475
Excluded based on Exclusion 14 - CCI (180 days)	-7	25,616	-47	82,796	-1,939	161,536
Final cohort		25,616		82,796		161,536

* Medicare database includes all patients using a novel oral anticoagulant and a subset of patients using warfarin during 2011-2017.

6. Variables

6.1 Exposure-related variables:

Study drug:

The study exposure of interest is initiation of dabigatran. Initiation will be defined by no use of dabigatran or a comparator in the prior 6 months before treatment initiation (washout period).

Comparator agents-

- Initiators of dabigatran (150mg) will be compared to initiators of-
 - Warfarin

6.2 Covariates:

- Age
- Sex
- Combined Comorbidity Index (CCI), measured over the baseline covariate assessment period, defined as 180 days prior to and including index date

Covariates listed above represent only a small subset of covariates that will ultimately be controlled for in the design and analysis. We use the covariates above only for initial feasibility analyses to judge whether there is likely to be sufficient overlap between treatment groups to proceed with the study. Remaining covariates are defined only after the study has passed the initial feasibility analysis and the initial power assessment and are listed in Table 1 (**Appendix B**).

6.3 Outcome variables and study follow-up:

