After review of initial feasibility and power analyses, complete creation of the remaining covariates (see Table 1 below for list of covariates). Again, using the dummy outcome of a 90-day gap in database enrollment, complete a 1:1 PS-matched analysis. The PS should include the complete list of covariates (excluding laboratory values, which are missing in some patients).

- Provide plot of PS distributions stratified by treatment group.

Note- Please refer to **Appendix B**.

- Report covariate balance after matching.

Note- For Table 1, please refer to **Appendix B**.

- Report reasons for censoring by treatment group.

	Overall	Referent	Exposure
Dummy Outcome	0 (0.00%)	0 (0.00%)	0 (0.00%)
Death	657 (0.84%)	369 (0.94%)	288 (0.74%)
Start of an additional exposure	2,760 (3.53%)	1,189 (3.04%)	1,571 (4.02%)
End of index exposure	62,039 (79.39%)	31,190 (79.83%)	30,849 (78.96%)
Specified date reached (Dec 17/Dec 18/Dec 19)	2,483 (3.18%)	1,281 (3.28%)	1,202 (3.08%)
End of patient enrollment	4,128 (5.28%)	1,938 (4.96%)	2,190 (5.61%)
Switch to other NOACs (for censoring) + nursing home admission	6,073 (7.77%)	3,103 (7.94%)	2,970 (7.60%)

- Report follow-up time by treatment group.

Median Follow-Up Time (Days) [IQR]			
Patient Group	Optum	Truven	Medicare
Overall Patient Population	98 [38-191]	98 [38-193]	98 [38-202]

Referent	98 [43-192]	98 [43-178]	98 [42-196]
Exposure	98 [38-190]	98 [38-220]	98 [38-211]

- Report overall risk of the primary outcome.

	Optum	MarketScan	Medicare	Pooled
Risk per 1,000 patients	4.57	5.20	6.04	5.64

10. Final Power Assessment

Date conducted:

- Re-calculate power in the appropriate excel table, using the revised number of matched patients from the PS-match in Section 9. All other parameters in the table should be the same as in Section 8. If the study is to be implemented in more than one database, copy and paste excel sheet to report power for each database separately and for the pooled analysis that uses data from all databases together. Power calculations are based on the formulas from Chow et al. (2008).
 - For dabigatran 150mg vs. warfarin
 - Pooled

Superiority Analysis		Non-inferiority Analysis	
Number of patients matched	78,140	Number of patients matched	78,140
Reference	39,070	Reference	39,070
Exposed	39,070	Exposed	39,070
Risk per 1,000 patients	5.64	Risk per 1,000 patients	5.64
Desired HR from RCT	0.66	Assumed HR from RCT	1
Alpha (2-sided)	0.05	Alpha (2-sided)	0.05
		Non-inferiority margin	1.46

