Other Medications												
Use of ACE inhibitors; n (%)	7,637 (33.7%)	997 (34.0%)	-0.01	23,436 (34.6%)	5,249 (35.2%)	-0.01	47,332 (34.8%)	8,768 (34.8%)	0.00	78405 (34.6%)	15014 (34.3%)	0.00
Use of ARBs; n (%)	4,045 (17.8%)	571 (19.4%)	-0.04	14,719 (21.7%)	3,547 (23.8%)	-0.05	26,443 (19.4%)	5,734 (22.7%)	-0.08	45207 (20.0%)	9852 (22.9%)	-0.07
Use of Loop Diuretics - United; n (%)	4,781 (21.1%)	482 (16.4%)	0.12	21,128 (31.2%)	3,432 (23.0%)	0.19	34,289 (25.2%)	4,812 (19.1%)	0.15	60198 (26.6%)	8726 (20.2%)	0.15
Use of other diuretics - United; n (%)	859 (3.8%)	91 (3.1%)	0.04	4,266 (6.3%)	730 (4.9%)	0.06	6,138 (4.5%)	869 (3.4%)	0.06	11263 (5.0%)	1681 (3.9%)	0.05
Use of nitrates-United; n (%)	1,267 (5.6%)	146 (5.0%)	0.03	6,398 (9.4%)	1,249 (8.4%)	0.04	10,986 (8.1%)	1,964 (7.8%)	0.01	18651 (8.2%)	3359 (7.8%)	0.01
Use of other hypertension drugs; n (%)	1,739 (7.7%)	228 (7.8%)	0.00	5,200 (7.7%)	1,037 (6.9%)	0.03	9,777 (7.2%)	1,817 (7.2%)	0.00	16716 (7.4%)	3082 (7.2%)	0.01
Use of digoxin- United; n (%)	3,142 (13.9%)	318 (10.8%)	0.09	13,308 (19.6%)	2,168 (14.5%)	0.14	20,843 (15.3%)	2,997 (11.9%)	0.10	37293 (16.5%)	5483 (12.7%)	0.11
Use of Anti-arrhythmics; n (%)	2,154 (9.5%)	459 (15.6%)	-0.18	9,822 (14.5%)	3,029 (20.3%)	-0.15	15,578 (11.4%)	4,366 (17.3%)	-0.17	27554 (12.2%)	7854 (18.2%)	-0.17
Use of COPD/asthma meds - United; n (%)	3,022 (13.3%)	435 (14.8%)	-0.04	12,353 (18.2%)	2,900 (19.4%)	-0.03	20,518 (15.1%)	4,170 (16.5%)	-0.04	35893 (15.8%)	7505 (17.4%)	-0.04
Use of statins; n (%)	12,189 (53.8%)	1,579 (53.8%)	0.00	37,940 (56.0%)	8,310 (55.7%)	0.01	74,659 (54.9%)	14,235 (56.4%)	-0.03	124788 (55.1%)	24124 (56.0%)	-0.02
Use of other lipid-lowering drugs; n (%)	1,345 (5.9%)	221 (7.5%)	-0.06	6,440 (9.5%)	1,567 (10.5%)	-0.03	9,683 (7.1%)	2,038 (8.1%)	-0.04	17468 (7.7%)	3826 (8.8%)	-0.04
Use of antiplatelet agents; n (%)	1,466 (6.5%)	282 (9.6%)	-0.11	8,223 (12.1%)	2,505 (16.8%)	-0.13	12,346 (9.1%)	3,435 (13.6%)	-0.14	22035 (9.7%)	6222 (14.4%)	-0.14
Use of heparin and other low-molecular weight heparins; n (%)	501 (2.2%)	11 (0.4%)	0.16	29 (0.0%)	2 (0.0%)	#DIV/0!	5,084 (3.7%)	125 (0.5%)	0.22	5614 (2.5%)	138 (0.3%)	0.19
Use of NSAIDs; n (%)	1,606 (7.1%)	290 (9.9%)	-0.10	5,269 (7.8%)	1,572 (10.5%)	-0.09	11,395 (8.4%)	3,015 (12.0%)	-0.12	18270 (8.1%)	4877 (11.3%)	0.11
Use of oral corticosteroids; n (%)	3,335 (14.7%)	475 (16.2%)	-0.04	12,514 (18.5%)	2,819 (18.9%)	-0.01	23,765 (17.5%)	4,688 (18.6%)	-0.03	39614 (17.5%)	7982 (18.5%)	-0.03

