...mean (sd)	0.08 (0.35)	0.09 (0.36)	-0.03	0.07 (0.40)	0.08 (0.35)	-0.03	0.11 (0.41)	0.13 (0.42)	-0.05	0.10 (0.40)	0.11 (0.39)	-0.03
...median [IQR]	0.00 [0.00, 0.00]	0.00 [0.00, 0.00]	0.00	0.00 [0.00, 0.00]	0.00 [0.00, 0.00]	0.00	0.00 [0.00, 0.00]	0.00 [0.00, 0.00]	0.00	0.00 (0.46)	0.00 (0.43)	0.00
Number of Cardiac biomarkers tests (tropnin, CK-MBs, Myoglobin, CPK)												
...mean (sd)	0.22 (0.91)	0.37 (1.23)	-0.14	0.21 (0.98)	0.32 (1.30)	-0.10	0.19 (0.49)	0.25 (0.56)	-0.11	0.20 (0.72)	0.28 (0.93)	0.00
...median [IQR]	0.00 [0.00, 0.00]	0.00 [0.00, 0.00]	0.00	0.00 [0.00, 0.00]	0.00 [0.00, 0.00]	0.00	0.00 [0.00, 0.00]	0.00 [0.00, 0.00]	0.00	0.00 (0.90)	0.00 (1.13)	0.00
Number of Ambulatory Blood pressure monitoring tests												
...mean (sd)	0.00 (0.03)	0.00 (0.03)	0.00	0.00 (0.04)	0.00 (0.04)	0.00	0.00 (0.02)	0.00 (0.04)	0.00	0.00 (0.03)	0.00 (0.04)	0.00
...median [IQR]	0.00 [0.00, 0.00]	0.00 [0.00, 0.00]	0.00	0.00 [0.00, 0.00]	0.00 [0.00, 0.00]	0.00	0.00 [0.00, 0.00]	0.00 [0.00, 0.00]	0.00	0.00 (0.04)	0.00 (0.04)	0.00
N of days on antihypertensive medications during baseline												
...mean (sd)	130.02 (68.95)	129.85 (66.94)	0.00	135.76 (65.79)	131.96 (67.63)	0.06	138.23 (64.13)	137.11 (64.13)	0.02	136.67 (65.13)	134.83 (65.56)	0.00
...median [IQR]	171.00 [89.00, 181.00]	168.00 [91.00, 181.00]	0.04	174.00 [110.00, 181.00]	171.00 [94.00, 181.00]	0.04	174.00 [122.00, 181.00]	173.00 [116.00, 181.00]	0.02	121.24 (74.47)	130.61 (73.42)	0.00
N of days in database anytime prior												
...mean (sd)	1,750.74 (1,238.00)	1,753.82 (1,191.57)	0.00	2,172.37 (1,246.30)	2,083.21 (1,203.95)	0.07	833.53 (537.51)	873.46 (457.48)	-0.08	1325.93 (889.77)	1352.52 (849.34)	0.00

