Appendix B

...mean (sd)	0.67 (0.86)	0.68 (0.84)	-0.01	0.25 (0.70)	0.24 (0.63)	0.02	0.68 (0.76)	0.68 (0.74)	0.00	0.53 (0.75)	0.52 (0.71)	0.01
...median [IQR]	0.00 [0.00, 1.00]	1.00 [0.00, 1.00]	-1.18	0.00 [0.00, 0.00]	0.00 [0.00, 0.00]	0.00	1.00 [0.00, 1.00]	1.00 [0.00, 1.00]	0.00	0.36 (0.81)	0.43 (0.77)	-0.09
Number of creatinine tests ordered												
...mean (sd)	0.07 (0.33)	0.07 (0.32)	0.00	0.05 (0.28)	0.05 (0.27)	0.00	0.10 (0.39)	0.09 (0.37)	0.03	0.08 (0.35)	0.07 (0.33)	0.03
...median [IQR]	0.00 [0.00, 0.00]	0.00 [0.00, 0.00]	0.00	0.00 [0.00, 0.00]	0.00 [0.00, 0.00]	0.00	0.00 [0.00, 0.00]	0.00 [0.00, 0.00]	0.00	0.00 (0.37)	0.00 (0.36)	0.00
Number of BUN tests ordered												
...mean (sd)	0.04 (0.23)	0.05 (0.25)	-0.04	0.03 (0.22)	0.03 (0.22)	0.00	0.06 (0.30)	0.05 (0.28)	0.03	0.05 (0.27)	0.04 (0.26)	0.04
...median [IQR]	0.00 [0.00, 0.00]	0.00 [0.00, 0.00]	0.00	0.00 [0.00, 0.00]	0.00 [0.00, 0.00]	0.00	0.00 [0.00, 0.00]	0.00 [0.00, 0.00]	0.00	0.00 (0.29)	0.00 (0.28)	0.00
Number of tests for microalbuminuria												
...mean (sd)	0.21 (0.70)	0.19 (0.64)	0.03	0.07 (0.37)	0.07 (0.37)	0.00	0.12 (0.41)	0.12 (0.39)	0.00	0.11 (0.42)	0.11 (0.41)	0.00
...median [IQR]	0.00 [0.00, 0.00]	0.00 [0.00, 0.00]	0.00	0.00 [0.00, 0.00]	0.00 [0.00, 0.00]	0.00	0.00 [0.00, 0.00]	0.00 [0.00, 0.00]	0.00	0.00 (0.46)	0.00 (0.44)	0.00
Total N distinct ICD9/ICD10 diagnoses at the 3rd digit level Copy												
...mean (sd)	3.02 (4.95)	3.04 (5.12)	0.00	2.23 (4.87)	2.21 (4.87)	0.00	4.18 (6.62)	4.08 (6.51)	0.02	3.40 (5.94)	3.34 (5.88)	0.01
...median [IQR]	0.00 [0.00, 5.00]	0.00 [0.00, 5.00]	0.00	0.00 [0.00, 2.00]	0.00 [0.00, 2.00]	0.00	0.00 [0.00, 6.00]	0.00 [0.00, 6.00]	0.00	0.00 (6.35)	0.00 (6.30)	0.00
For PS												
Hemorrhagic stroke+Other cerebrovascular disease+Cerebrovascular procedure (for PS); n (%)	45 (1.6%)	52 (1.9%)	-0.02	297 (2.1%)	316 (2.3%)	-0.01	416 (1.9%)	398 (1.8%)	0.01	758 (1.9%)	766 (2.0%)	-0.01
Occurrence of creatinine tests ordered (for PS); n (%)	148 (5.3%)	154 (5.5%)	-0.01	495 (3.5%)	495 (3.5%)	0.00	1,648 (7.4%)	1,562 (7.0%)	0.02	2291 (5.9%)	2211 (5.7%)	0.01
Occurrence of BUN tests ordered (for PS); n (%)	95 (3.4%)	103 (3.7%)	-0.02	311 (2.2%)	333 (2.4%)	-0.01	1,063 (4.8%)	1,001 (4.5%)	0.01	1469 (3.8%)	1437 (3.7%)	0.01
Occurrence of chronic renal insufficiency w/o CKD (for PS)v2; n (%)	0 (0.0%)	0 (0.0%)	#DIV/0!	0 (0.0%)	0 (0.0%)	#DIV/0!	0 (0.0%)	0 (0.0%)	#DIV/0!	0 (0.0%)	0 (0.0%)	#DIV/0!

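### The written propensity-score specification shows no index-year term although entry spans 7.2 to 9.2 years; adding one is a cheap improvement (separate and minor: check digoxin in the MarketScan score)

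*Combined protocol and SAP*

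**What the plan says.** Section 9 (Balance Assessment) specifies the score used for 1:1 matching: "The PS should include the complete list of covariates (excluding laboratory values, which are missing in some patients". Section 6.2 says where the list is: "Remaining covariates are defined only after the study has passed the initial feasibility analysis and the initial power assessment and are listed in Table 1". Read together, Table 1 in Appendix B is the written specification of the propensity score.

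Section 5.2.1 opens entry on 19 October 2010 in all three databases and closes it at the end of 2017 (Medicare), 2018 (MarketScan) or 2019 (Optum: "December 31, 2019 (end of available data"). The footnote to the flowchart in Section 5.3 adds: "Medicare database includes all patients using a novel oral anticoagulant and a subset of patients using warfarin during 2011-2017". No sampling fraction by year is given.

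Table 1 also has a block of combined rows marked as built for the score, such as "Hemorrhagic stroke+Other cerebrovascular disease+Cerebrovascular procedure (for PS); n". Digoxin has its own row, "Use of digoxin- United; n". The row nearest to calendar time is "N of days in database anytime prior", which measures length of look-back.

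**The concern.** If dabigatran and warfarin starters entered at different times within a window this long, any change over the years in stroke risk, care or measurement is mixed with the drug effect. The plan's own definitions show how measurement can depend on date. Exclusion 3i in Appendix A uses malignant hypertension with no ICD-10 code, and hypertensive urgency or crisis with no ICD-9 code. In Medicare, which supplies 22,320 of the 39,070 matched pairs (57%), all users of novel anticoagulants are present but only some warfarin users. The arms could therefore differ in date through data acquisition alone. No legible Table 1 row, and no named row in the Section 14 shells, would reveal this.

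The digoxin point is separate and is not evidence about calendar time. A covariate that the plan requires in the score should move towards balance when the score is matched. If it hardly moves in one database, the reported balance may belong to a different score from the one Section 9 specifies.

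**Working it through.** **Entry windows** (Section 5.2.1), as days from 19 October 2010 divided by 365.25:
- Medicare, to 31 December 2017: 2,630 / 365.25 = 7.20 years
- MarketScan, to 31 December 2018: 2,995 / 365.25 = 8.20 years
- Optum, to 31 December 2019: 3,360 / 365.25 = 9.20 years

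**Search of Table 1.** Neither the unmatched nor the PS-matched copy has a legible row for index year, quarter or date. In the copy reviewed, the tables break off in places. Most breaks in one copy are filled by the other. The only stretch lost from both lies in the medication block, between antidepressants and anxiolytics.

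**Indirect check 1: end-of-data censoring** (Section 9, row "Specified date reached (Dec 17/Dec 18/Dec 19"). The counts are 1,281 warfarin and 1,202 dabigatran of 39,070 each, which reproduces the printed 3.28% and 3.08%. With pooled proportion 2,483 / 78,140 = 0.0318, z = (0.03279 - 0.03077) / sqrt(0.0318 × 0.9682 × 2 / 39,070) = 1.6. This sees only patients still followed when the data end.

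**Indirect check 2: mean prior days in database, PS-matched Table 1.**

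| Database | Warfarin | Dabigatran | Difference (days) |
|---|---|---|---|
| Optum | 1,737.28 | 1,752.47 | -15.2 |
| MarketScan | 2,106.30 | 2,104.50 | +1.8 |
| Medicare | 860.39 | 859.94 | +0.5 |

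These are close, but the row is itself on the covariate list, so matching should balance it whatever the index dates. It also depends on how long patients were enrolled.

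**Digoxin.** Standardized difference = (p_w - p_d) / sqrt([p_w(1 - p_w) + p_d(1 - p_d)] / 2), with w warfarin and d dabigatran. MarketScan has 67,790 and 14,929 patients before matching and 13,960 per arm after.
- Before: 13,308 / 67,790 = 0.1963 and 2,168 / 14,929 = 0.1452, giving 0.136 (printed 0.14).
- After: 2,692 / 13,960 = 0.1928 and 2,018 / 13,960 = 0.1446, giving 0.129 (printed 0.13).

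Other MarketScan drug rows with a gap of similar size before matching, by the same formula:

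| Row | Before | After |
|---|---|---|
| Digoxin | 0.136 | 0.129 |
| Loop diuretics | 0.185 | 0.027 |
| Anti-arrhythmics | -0.153 | 0.021 |
| Antiplatelet agents | -0.133 | 0.003 |

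Digoxin improved elsewhere: 0.092 to 0.019 in Optum and 0.100 to 0.048 in Medicare. Pooled, it went from 0.106 to 0.077. Loop diuretics also appear in a combined row built for the score; no legible combined row contains digoxin.

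**Size of the digoxin effect.** The documents give no risk ratio (RR) for digoxin and the outcome, so 1.25 to 2 is assumed. The bias factor is [1 + p_d(RR - 1)] / [1 + p_w(RR - 1)].
- Pooled, with p_d = 4,899 / 39,070 = 0.1254 and p_w = 5,944 / 39,070 = 0.1521: 0.994 at RR 1.25 and 0.977 at RR 2.
- MarketScan alone: 0.988 and 0.960.

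At the planned 440.7 events and hazard ratio 0.66, events split 175.2 to 265.5, and the standard error of the pooled log hazard ratio is sqrt(1/175.2 + 1/265.5) = 0.097. The pooled shift is then 0.07 to 0.24 standard errors.

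**The case against.** The strongest reply is that Table 1 is not the fitted model. It contains combined rows made for the score alongside their components, and the digoxin finding itself suggests that a listed row may not have been used as listed. The fitted models sit behind platform links, and the design diagram is not visible in the copy reviewed. All of this stands. A reader might infer that index year was left out of the fitted score, but the documents support only the statement that it is not legible in the written specification.

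A reader might also infer that the arms are out of step in time and try to size the bias from the unmatched gaps in prior days (for example 2,172 against 2,083 in MarketScan). That fails: the analysis is of matched patients, whose means are nearly equal, and the row is a poor proxy for index date in either cohort. No bias figure should be taken from it.

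The Medicare footnote speaks of 2011-2017, which would make that window at most 7.0 years instead of 7.2. This changes nothing of substance.

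Echocardiogram stays near 0.10 after matching (-0.103 Optum, -0.095 MarketScan, -0.088 Medicare) and might be read as a second omitted covariate. It started at -0.322, -0.314 and -0.336, so matching cut it by 68% to 74%, which is not the pattern of a variable left out.

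On digoxin, it is fair to say that this is one covariate in one database, that the plan states no balance threshold, and that Section 9 already requires the full list. The request is therefore to confirm compliance.

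**Conclusion.** The point holds as a low-cost improvement. The written specification has no legible calendar-time term over entry windows of 7.2 to 9.2 years, and Medicare warfarin users are a subset of unknown distribution over time. Neither the content of the fitted scores nor the index-date balance of the matched arms can be determined from the documents. The two indirect checks show no gross mismatch, but both are weak. The size and sign of any bias are unknown, and it may be zero. The case for acting is that index date is known for every patient, so the check is complete and can be made without looking at outcomes.

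The MarketScan digoxin result is exact as arithmetic and minor in effect. It would fit digoxin being absent from that database's score, but does not prove it. If digoxin users have the higher risk, the residual gap lowers the hazard ratio and so favours dabigatran, by about 0.6% to 2.3% pooled under the assumed risk ratios.

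**What to change.** 1. Add index calendar year (or quarter) as a categorical term to each database's propensity score. If the fitted score already contains it, say so in Section 9.
2. Show index year by arm, before and after matching, in Table 1. The Section 14.1 shell is open-ended, so a row can be added.
3. Refresh the balance and power tables before outcomes are compared. Sections 13.1 and 13.2 are still blank.
4. Confirm that digoxin entered the MarketScan score as Section 9 requires, and re-match if it did not. If it stays unbalanced, adjust for it in the outcome model when Section 13.1 specifies one.

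The cost is one re-match per database, new balance and power tables, and a refreshed review under the stop in Section 10. If the term is already in the scores, items 1 to 3 reduce to a sentence and a table row. A few pairs may be lost; the number cannot be given without the index-year distribution. For reference, matching now leaves 146 of 2,936 (Optum), 969 of 14,929 (MarketScan) and 2,910 of 25,230 (Medicare) dabigatran patients unmatched, in all 4,025 of 43,095 (9.3%).

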6.3.2 Study follow-up

Both as-treated (AT) and intention-to-treat (ITT) analyses will be conducted with treatment defined as the index drug on the day of cohort entry. Because adherence in the real-world databases is expected to be much worse than in the trial, the AT analysis is the **primary** analysis, as it targets the relative hazard of outcomes on treatment.

For the AT analyses, the follow-up will start the day after initiation of apixaban and comparator and will continue until the earliest date of the following events:

- The first occurrence of the outcome of interest, unless otherwise specified for selected outcomes,
- The date of end of continuous registration in the database,
- End of the study period,
- Measured death event occurs,

- Nursing home admission
 - Nursing home admissions are considered a censoring event because the data sources utilized typically provide little to no data on a patient, particularly on drug utilization, after admission. We will utilize this as an exclusion reason for cohorts for the same reason.
- The date of drug discontinuation, defined as the date of the last continuous treatment episode of the index drug (dabigatran and comparator) plus a defined grace period (i.e., 10 days after the end of the last prescription's days' supply in main analyses).
- The date of augmentation or switching from exposure to comparator or vice versa or augmentation/switching to any other NOAC (e.g. switching from dabigatran or warfarin to apixaban would be a censoring event);
 - A dosage change on the index treatment does not fulfill this criterion
 - An added treatment that is not part of the exposure or comparator group does not fulfill this criterion
- Dispensing of a fibrinolytic agent

For the intention-to-treat (ITT) analyses, the censoring based on the augmentation/switching and treatment discontinuation will be replaced with a maximum allowed follow-up time of 365 days.

7. Initial Feasibility Analysis

Action report name:

For dabigatran vs. warfarin

Optum- <https://bwh-dope.aetion.com/projects/details/707/results/59579/result/0>

Marketscan- <https://bwh-dope.aetion.com/projects/details/708/results/59601/result/0>

Medicare- <https://bwh-dope.aetion.com/projects/details/709/results/59602/result/0>

Date conducted: 10/5/20 (Medicare 10/6/20)

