Complete Aetion feasibility analysis using age, sex, and CCI as the only covariates and the primary endpoint (Section 6.3.1) as the outcome. No measures of association will be computed nor will incidence rates stratified by treatment group.

- Report patient characteristics by treatment group
- Report summary parameters of study population
- Report median follow-up time by treatment group
- Report reasons for censoring in the overall study population

8. Initial Power Assessment

Action report name:

For dabigatran vs. warfarin

Optum- <https://bwh-dope.aetion.com/projects/details/707/results/53772/result/0>

Marketscan- <https://bwh-dope.aetion.com/projects/details/708/results/53771/result/0>

Medicare- <https://bwh-dope.aetion.com/projects/details/709/results/53770/result/0>

Date conducted: 05/11/2020

In order to complete the initial power analysis, the dummy outcome of a 90-day gap in database enrollment will be used. This outcome is used to ensure that no information on the comparative risks of the outcomes of interest are available at this stage. Complete a 1:1 PS-matched comparative analysis using this outcome. PS should include only 3 covariates: age, sex, and combined comorbidity index. Power calculations are based on the formulas from Chow et al. (2008).

- Stop analyses until feasibility and power are reviewed by primary investigators and FDA. Reviewers evaluate the results of the analyses described above in Sections 7 and 8, including numbers of patients, patient characteristics, follow-up time, and reasons for censoring by treatment group, as well as overall rates of outcomes and study power. These parameters are re-evaluated and reported in the subsequent sections, after incorporating feedback and refining the protocol.
- Stop analyses until feasibility and power are reviewed by primary investigators, FDA, and assigned members of advisory board.

Reviewed by PI:	[name]	Date reviewed:	6/3/20
Reviewed by FDA:	[name]	Date reviewed:	6/30/20
Reasons for stopping analysis (if required):			

9. Balance Assessment

Action report links:

Optum: <https://bwh-dope.aetion.com/projects/details/707/results/59580/result/0>

Marketscan: <https://bwh-dope.aetion.com/projects/details/708/results/59603/result/0>

Medicare: <https://bwh-dope.aetion.com/projects/details/709/results/59604/result/0>

Date conducted: 10/5/20 (Medicare 10/6/20)

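### Do the unlabelled outcome risks and the October run dates undermine the Section 10 power tables?

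*Combined protocol and SAP*

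**What the plan says.** The plan assesses power in stages, keeping the comparative result hidden.

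- **Section 7** (initial feasibility): "Complete Aetion feasibility analysis using age, sex, and CCI as the only covariates and the primary endpoint (Section 6.3.1) as the outcome". No association measures and no rates by treatment group are allowed. The run is dated 10/5/20, Medicare 10/6/20.
- **Section 8** (initial power): "In order to complete the initial power analysis, the dummy outcome of a 90-day gap in database enrollment will be used". It carries the line "Date conducted: 05/11/2020". Those reviewing Sections 7 and 8 are to see overall outcome rates as well as power; reviews are recorded on 6/3/20 and 6/30/20. The section adds: "These parameters are re-evaluated and reported in the subsequent sections, after incorporating feedback and refining the protocol".
- **Section 9** (balance): "Again, using the dummy outcome of a 90-day gap in database enrollment, complete a 1:1 PS-matched analysis". Its outputs include the item "Report overall risk of the primary outcome", followed by the four risks. Its run dates are the same as those of Section 7.
- **Section 10** (final power): the matched number is updated and, for the rest, "All other parameters in the table should be the same as in Section 8". Its own date field is blank. Reviews are recorded on 9/8/20 and 9/29/20.

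**The concern.** Three things look wrong on a first reading.

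1. The risk determines the expected events in every power table, but the two sections that appear to supply it (8 and 9) describe runs on a dummy outcome. The natural assumption, that the Section 9 figure is the risk in the matched cohort, fails for Optum: no whole number of events among 5,580 patients gives 4.57 per 1,000.
2. Section 8 says parameters will be re-evaluated later, while Section 10 says they stay as in Section 8.
3. The listed Section 7 and Section 9 runs come 27 and 6 days after the two final reviews.

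Section 10 is a stop point for the investigators, FDA and the advisory board. If the matched number or the risk had been replaced after sign-off, the approval would not belong to the figures shown. If the risk were badly wrong, the study could have gone ahead on power it did not have.

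**Working it through.** **Reproducing the plan's figures.** Inputs from Section 10: matched N, risk per 1,000, hazard ratio 0.66 for superiority, margin 1.46 with true ratio 1 for non-inferiority, two-sided alpha 0.05.

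Expected events: d = N × risk / 1,000.

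Superiority power = Φ(√(d/4)·|ln 0.66| − 1.96) + Φ(−√(d/4)·|ln 0.66| − 1.96).

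Non-inferiority power = Φ(√(d/4)·ln 1.46 − 1.96).

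| | N | Risk | d | Superiority | Non-inferiority |
|---|---|---|---|---|---|
| Pooled | 78,140 | 5.64 | 440.7096 | 0.9918 | 0.9779 |
| Optum | 5,580 | 4.57 | 25.5006 | 0.1825 | 0.1576 |
| MarketScan | 27,920 | 5.20 | 145.184 | 0.7066 | 0.6255 |
| Medicare | 44,640 | 6.04 | 269.6256 | 0.9267 | 0.8743 |

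All eight agree with the printed powers, and the event figures are exactly N × risk. There is no arithmetic error.

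**Which cohort gave the risk?** A printed 4.57 means a value from 4.565 to 4.575. Over 5,580 patients that is 25.47 to 25.53 events, which contains no integer (25 gives 4.48, 26 gives 4.66). So Optum's figure does not come from the printed match. The unmatched Appendix B total fits: 117 / (22,665 + 2,936) = 117/25,601 = 4.570. MarketScan and Medicare fit too (430/82,719 = 5.198; 974/161,317 = 6.038), but these are weak tests. The rounding window is N × 0.01/1,000 events wide: 0.26 for Optum, 0.83 for MarketScan and 1.61 for Medicare, so for Medicare some integer always fits. The evidence is consistent with a pre-match cohort but does not prove it; an earlier match of unprinted size is also possible. A pre-match risk is what Section 7 would yield.

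**The dates.** Section 8 has the first reviews (6/3/20 and 6/30/20) consider overall outcome rates, which presupposes a primary-endpoint run by then. Section 9 is to be done only after that first review. Yet the listed reports for Sections 7 and 9 have adjacent numbers (Optum 59579 and 59580; MarketScan 59601 and 59603; Medicare 59602 and 59604), well above those of Section 8 (53770 to 53772). An original feasibility run would not sit next to the later balance run. Re-running both together and refreshing the links would produce this pattern.

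**How wrong could the risk be?** Events for 80% power:

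- superiority: 4 × (1.960 + 0.842)² / (ln 0.66)² = 181.8, so 182;
- non-inferiority: 4 × (1.960 + 0.842)² / (ln 1.46)² = 219.2, so 220.

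Over 78,140 patients these are 182/78.14 = 2.33 and 220/78.14 = 2.82 per 1,000, against 5.64 printed. Halving the pooled risk leaves 220.4 events and powers of 0.870 and 0.802. For Medicare alone the break-even risks are 182/44.64 = 4.08 and 220/44.64 = 4.93, against 6.04. Optum and MarketScan are below 80% as printed.

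**The case for a change.** The strongest case for acting is that a staged, publicly registered protocol earns trust by showing what was reviewed and when. On paper, neither the matched number nor the risk can be tied to a run that precedes the final reviews. The earlier run is an inference, since the document does not list one. Day/month confusion does not explain the order, because 6/30/20 and 9/29/20 have only one reading. A label and a date note would cost almost nothing.

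Those facts stand. They do not show that the risk lacks a source: the dummy outcome in Sections 8 and 9 is a masking device, and Section 7 supplies the overall rate. Nor do Sections 8 and 10 conflict. The first concerns descriptors to be reported again, the second the inputs to the power sheet; if the risk was unchanged, both are met.

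One could go further and recompute power on the view that the risk comes from a pre-match cohort that is 84% warfarin (226,542 of 269,637). That would assume both an unconfirmed source and a warfarin risk unaffected by matching, although matching lowers the pooled mean age of warfarin users from 78.86 to 75.98. The tolerances above need neither assumption.

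Medicare non-inferiority power is the most exposed result: it drops below 80% if the risk is about 18% lower than printed (4.93/6.04 = 0.816). Section 10 sets no power threshold, however, and the smaller databases were already below 80% in the tables shown, with no reason for stopping recorded.

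**Conclusion.** The concern identifies a real gap in the record but gives no reason to change the plan. The four risks lack a label, and the October dates lack a note saying whether they mark re-runs. Analysts with platform access can settle both from the linked reports and the implementation history that Section 2 says is archived.

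The powers are correct for their inputs, and the pooled conclusion survives a halving of the risk. No outcome definition, follow-up rule, matching step or analysis depends on the answer. Labelling the risks and annotating the dates would tidy the file without altering what is done or concluded.

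This rests on two readings that the documents support but do not state: that Section 7 supplied the overall risk, and that an earlier, unlisted run was the one reviewed. The power tolerance depends on neither; it takes the printed matched numbers and effect assumptions as given and uses 80% as a conventional yardstick.
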